 To be completed during applicable study visits before study drug administration.

 Adverse Events will be collected after Informed Consent signature through the end of the Follow-Up Period (12 weeks after the last dose of study drug)  
[REDACTED].

 Study drug is administered by study staff, every 4 weeks ( $\pm$  5 days) during the applicable study visits. One pre-filled syringe will be administered at each visit.

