### 10.1 Definition of adverse events and reporting requirements

#### 10.1.1 Adverse events

An adverse event (AE) is any untoward medical occurrence (e.g. any unfavorable and unintended sign [including abnormal laboratory findings], symptom or disease) in a subject or clinical investigation subject after providing written informed consent for participation in the study. Therefore, an AE may or may not be temporally or causally associated with the use of a medicinal (investigational) product.

The investigator has the responsibility for managing the safety of individual subject and identifying adverse events.

Novartis qualified medical personnel will be readily available to advise on trial-related medical questions or problems.

The occurrence of adverse events must be sought by non-directive questioning of the subject at each visit during the study. Adverse events also may be detected when they are volunteered by the subject during or between visits or through physical examination findings, laboratory test findings, or other assessments.

Adverse events must be recorded in the Adverse Events CRF under the signs, symptoms or diagnosis associated with them, accompanied by the following information (as far as possible) (if the event is serious refer to [Section 10.1.2](#)):

1. Adverse events will be assessed and graded according to the most current version of the Common Terminology Criteria for Adverse Events (CTCAEs)
2. its relationship to the study treatment. If the event is due to lack of efficacy or progression of underlying illness (i.e. progression of the study indication) the assessment of causality will usually be 'Not suspected'. The rationale for this guidance is that the symptoms of a lack of efficacy or progression of underlying illness are not caused by the trial drug, they happen in spite of its administration and/or both lack of efficacy and progression of underlying disease can only be evaluated meaningfully by an analysis of cohorts, not on a single subject

3. its duration (start and end dates) or if the event is ongoing, an outcome of not recovered/not resolved must be reported.
4. whether it constitutes a SAE (see [Section 10.1.2](#) for definition of SAE) and which seriousness criteria have been met
5. action taken regarding with study treatment.

All adverse events must be treated appropriately. Treatment may include one or more of the following:

- Dose not changed
- Drug interrupted/withdrawn

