### **Adverse events**

The Medical Dictionary for Regulatory Activities will be used to code all adverse events (AEs). A treatment-emergent adverse events (TEAE) is defined as any adverse event that develops after initiation of study treatment until the end of the last study visit or any event already present that worsens following exposure to the study treatment until the end of the last study visit. Subject incidence rates of TEAEs will be tabulated by SOC and PT by treatment group, separately for the double-blind period [REDACTED]. Tables of TEAE by maximum toxicity grade, fatal AEs, serious AEs, AEs leading to withdrawal from investigational drug, treatment-related AEs, and serious treatment-related AEs will also be presented in a similar format as TEAE. Additionally, a listing of subject with TEAE will be presented. The TEAEs identified as potential risk will be summarized separately.

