2.1.1.2 Study points of reference

Study day

Study Day 1 is defined as the first investigational product (IP) dose date. For subjects who are randomized but not dosed after randomization, the Study Day 1 is defined as the date of randomization.

Study Day is defined as the number of days from Study Day 1.

Before Study Day 1:

Study Day = (Date of Interest – Date of Study Day 1)

On or after Study Day 1:

Study Day = (Date of Interest – Date of Study Day 1) + 1

Therefore the day prior to Study Day 1 is -1.

Baseline

The baseline period for efficacy endpoints collected by the daily eDiary (e.g., monthly migraine days, acute migraine-specific medication days, [REDACTED], ...) is defined as the period between week -4 visit (when eDiary device is dispensed to the subject for daily data capture) and the day prior to study day 1 (study day 1 is not included).

A baseline for PRO [REDACTED], BDI-II, MIDAS) and safety (including C-SSRS) values refers to the last evaluable measurement prior to the first administration of the study drug, irrespective of re-screening. In this case, baseline values will be the values obtained on day 1 (date of first administration of study drug or randomization day if the subject was not dosed after randomization) or on an earlier visit (scheduled or unscheduled) which is the closest to day 1 visit, if the assessment was not done on day 1. In case of multiple assessments on the same day, the first one will be considered for PRO and the latest one for safety; for C-SSRS the first complete assessment performed with the electronic version (“Since last visit” recall period) or supplemental data collected on the CRF page will be used.

Note: Assessments on the day of randomization are assumed to have been taken as per protocol, i.e. if the assessment should be performed before dosing, the assessment will be treated as pre-dose as per protocol. Practically, i.e. that the time part of the date/time entry will be ignored. Exception: In case there is a protocol deviation or a comment that specifically indicates that the assessment has been taken post-dose, the assessment will not be treated as pre-dose.

C-SSRS screening value

Screening value for C-SSRS refers to the last evaluable complete assessment for the recall period “Lifetime” prior or on day 1.

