2.1.4.2 Safety endpoints

Subject Incidence

The subject incidence for a given event in a given period is defined as the number of subjects with at least one reported occurrence of the event divided by the number of subjects who entered that period. For subjects with multiple occurrences of the same event, the event will only be counted once per subject.

Exposure-Adjusted Subject Incidence Rate

The exposure-adjusted subject incidence rate for a given event in a given period is defined as the number of subjects with at least one reported occurrence of the event in a given time period divided by total subject years at risk in that period. The time at risk for each subject will differ for each adverse event. For subjects with events, only the time until the first event contributes to the total subject years at risk. For subjects who do not experience the event, the time at risk will be up to the last available visit. This rate will be presented per 100 subject years. For subjects with multiple occurrences of the same event, the event will be only counted once per subject.

Treatment-Emergent Adverse Event (TEAE)

Adverse Events (AEs) recorded on the Adverse Events eCRF page that occurs on or after first dose of investigational product and up to and including end of study.

Serious Adverse Event (SAE)

SAEs determined by the flag indicating if the adverse event is serious on the Adverse Events eCRF page will include those that occur after signing of the informed consent and up to and including end of study.

Treatment-Emergent Serious Adverse Event

A treatment-emergent serious adverse event is an SAE considered to be treatment-emergent.

Treatment-Related Adverse Event

A treatment-related AE is defined as a treatment-emergent adverse event that is considered by investigators to have reasonable possibility that it may have been caused by IP as determined by the flag indicating that there is a reasonable possibility that the AE is related to investigational product on the Adverse Events eCRF page.

Treatment-Related Serious Adverse Event

A treatment-related serious adverse event is an SAE considered to be treatment-related.

Adverse Event leading to discontinuation of study treatment

An AE leading to discontinuation of study treatment will be identified by the item “Action Taken With Study Treatment” on AE page of CRF when it’s reported as “Drug withdrawn”.

Serious Adverse Event leading to discontinuation of study treatment

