5.1.2 AE and Concomitant medication date imputation

Missing or incomplete dates will be listed as it is in any listings.

Incomplete start date of an adverse event or concomitant medication taken will be handled by following rule:

	Missing	Imputation	Exception
Start date (AE, concomitant medication)	Day	01	Default to Study Day 1 if an adverse event starts the same year and month as Study Day 1
	Day/Month	01Jan	Default to Study Day 1 if an event started the same year as Study Day 1
	Day/Month/Year	No imputation	

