5.1.3 Prior therapies date imputation

For prior medications with a stop date prior to the treatment phase (not possible to be at or after first drug administration), the start date will be imputed as the earliest possible start date and the stop date as the latest possible stop date:

For a missing/incomplete start date the minimum of the following will be imputed:

- The maximum of the earliest possible start date and the imputed birth date;
- The latest possible start date;
- The latest possible stop date.

For a missing/incomplete stop date the maximum of the following will be imputed:

- The minimum of the latest possible stop date and the date of first drug administration - 1;
- The earliest possible stop date;
- The earliest possible start date.

Here, the earliest (latest) possible date is defined as:

- The date itself if it is complete;
- The date of the first (last) day of the month, if month and year are available but day is missing;
- The date of the first (last) day of the year, if year is available but day and month are missing;
- A very early (late) date, e.g., 01JAN1000 00:00hrs (01JAN3000 23:59hrs), if the date is completely missing.

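### SAP 5.1.2 sets partial adverse event start dates to Study Day 1 without checking the stop date, so an event that ended before dosing is counted as treatment-emergent

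*SAP*

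**What the plan says.** SAP 5.1.2 gives one table for incomplete start dates. If only the day is missing, the first of the month is used, with this exception: "Default to Study Day 1 if an adverse event starts the same year and month as Study Day 1". If day and month are missing, 1 January is used, with this exception: "Default to Study Day 1 if an event started the same year as Study Day 1". The table has no condition on the stop date. The section also says that listings will show incomplete dates as recorded.

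Three other statements decide what the imputed date does:

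- SAP 2.1.1.2: "Study Day 1 is defined as the first investigational product (IP) dose date".
- SAP 2.1.4.2 defines a treatment-emergent AE as a recorded AE "that occurs on or after first dose of investigational product and up to and including end of study".
- Protocol 12.5.2, under adverse events, defines it as "any adverse event that develops after initiation of study treatment until the end of the last study visit", or an existing event that worsens after exposure.

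Pre-dose AEs will be in the database. Protocol Table 8-1, footnote 14, says: "Adverse Events will be collected after Informed Consent signature through the end of the Follow-Up Period". Protocol 10.1.1 asks for each event's "its duration (start and end dates) or if the event is ongoing", so stop dates are available to the derivation.

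The next section, SAP 5.1.3, does use the stop date, but for prior medications: "For a missing/incomplete start date the minimum of the following will be imputed". One of the dates listed there is the latest possible stop date.

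**The concern.** Moving a partial start date to Day 1 is a sensible conservative choice when it is unclear whether the event began before or after dosing. Once the recorded stop date is before Day 1 there is no such doubt, because the event cannot have started on treatment. The rule as written still moves it to Day 1.

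Two things follow. The derived record has a start later than its stop, and the event is counted as treatment-emergent when the protocol definition excludes it. SAP section 4 declares no change from the protocol analyses, so this is not a declared departure. In the exposure-adjusted rates of SAP 2.1.4.2, a subject with an event contributes time only up to the first occurrence. A false Day 1 event therefore adds an event and removes almost all of that subject's time at risk for that term.

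**Working it through.** The documents give no figure on this point, so there is none to reproduce. The check has two parts.

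**1. The rule applied literally.** The dates are an assumed example with Study Day 1 = 20 June 2020. Treatment-emergent status follows SAP 2.1.4.2 (start on or after Day 1). The last column adds the stop-date condition proposed under the fix.

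| Recorded start | Recorded stop | Start under SAP 5.1.2 | Treatment-emergent | Start after stop | With stop-date condition |
|---|---|---|---|---|---|
| June 2020, day missing | 10 June | 20 June | yes | yes, by 10 days | 1 June, not emergent |
| 2020 only | 10 June | 20 June | yes | yes, by 10 days | 1 January, not emergent |
| 2020 only | 25 May | 20 June | yes | yes, by 26 days | 1 January, not emergent |
| June 2020, day missing | 25 June | 20 June | yes | no | unchanged |
| June 2020, day missing | none | 20 June | yes | not applicable | unchanged |
| May 2020, day missing | 30 May | 1 May | no | no | unchanged |

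The first three rows are wrong and the last three are right. The error needs both a partial start that matches Day 1 on its known part and a stop date known to precede Day 1.

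**2. How many events could be involved.**

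- Pre-dose window: 42 days (protocol Table 8-1; 2 weeks of screening plus 4 weeks of baseline).
- Share of that window in the same calendar month as Day 1, with Day 1 spread evenly over a 30-day month: mean (0 + 1 + … + 29)/30 = 14.5 days, and 14.5/42 = 35%. Counting actual calendar days for every Day 1 date over 730 days from 1 January 2020 also gives 35%.
- Share in the same calendar year, by the same count: 94%. This is the share relevant to year-only dates.
- Assumed, not in the documents: 110 pre-dose AEs (20% of 550), with onsets spread evenly over the window, and a missing start day in 1% to 5% of them.
- Day-missing events sent to Day 1: 110 × 0.01 × 0.35 = 0.4, to 110 × 0.05 × 0.35 = 1.9.

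This count applies only the first of the two conditions. It includes AEs still ongoing at Day 1 and AEs with no usable stop date, for which the default is proper. Same-month events are also the ones closest to dosing, and so the most likely to overlap it. The range of 0.4 to 2 is therefore an upper bound under these assumptions. Year-only dates are not in it, since there is no basis for assuming how often they occur.

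For scale, with 275 subjects planned per arm, one false event changes the incidence of that term in its arm by at most 1/275 = 0.36 percentage points.

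**The case against.** The strongest reply is that the SAP never says an imputed start overrides a complete stop date when treatment-emergent status is decided. An event that ended before dosing meets neither definition in substance. Protocol 11.1 and 11.2 provide automatic checks and queries for discrepancies and missing values, and a further check may sit in programming specifications that are not part of these documents. Such records should also be rare within a window of about six weeks.

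The point about rarity stands, and a check elsewhere cannot be excluded. But the SAP is the governing text. Its rule gives a definite date, no other AE rule in either document corrects it, and a programmer who follows it exactly gets the wrong classification. Impossible dates would be confined to derived variables, since listings show the dates as recorded.

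A reader might also infer that the same fault affects concomitant medications, because they share the table. The documents do not support that for medications that stopped before dosing. SAP 5.1.3 covers them and already limits the imputed start by the latest possible stop date. SAP 2.1.4.2 also counts a drug as concomitant only if it was given at least once from first dose onward.

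**Conclusion.** The point holds for AEs, as a minor one. For an AE with a partial start matching Day 1 and a recorded stop before Day 1, SAP 5.1.2 gives a wrong value, and the resulting classification contradicts protocol 12.5.2.

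The number affected cannot be derived from the documents. About 0.4 to 2 day-missing events is an upper bound that rests on the assumed 110 pre-dose AEs and 1% to 5% partial dates. The true number may well be zero.

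Two stronger readings are tempting and should not be drawn. One is that every pre-dose AE moved to Day 1 is misclassified. That is true only of those known to have ended before Day 1; for the rest the default is reasonable. The other is that the rule biases the safety comparison. It is identical in both arms, and SAP 2.7 plans no between-group testing of safety data, so nothing in the documents points to a systematic difference or to an effect on any trial conclusion.

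**What to change.** Add one condition to SAP 5.1.2, for adverse events only:

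*The Study Day 1 default applies only if the AE stop date is missing, the event is ongoing, or the stop date could be on or after Study Day 1. Otherwise the start is imputed as the earliest possible date, no later than the latest possible stop date, and the event is not treatment-emergent.*

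This carries the logic of SAP 5.1.3 over to AEs. In the examples it removes all three false classifications and leaves the legitimate Day 1 defaults as they are. No change is needed for medications stopped before dosing. The cost is this short addition to the SAP and one condition in the derivation program, with no new data to collect.

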5.1.3 Prior therapies date imputation

For prior medications with a stop date prior to the treatment phase (not possible to be at or after first drug administration), the start date will be imputed as the earliest possible start date and the stop date as the latest possible stop date:

For a missing/incomplete start date the minimum of the following will be imputed:

- The maximum of the earliest possible start date and the imputed birth date;
- The latest possible start date;
- The latest possible stop date.

For a missing/incomplete stop date the maximum of the following will be imputed:

- The minimum of the latest possible stop date and the date of first drug administration - 1;
- The earliest possible stop date;
- The earliest possible start date.

Here, the earliest (latest) possible date is defined as:

- The date itself if it is complete;
- The date of the first (last) day of the month, if month and year are available but day is missing;
- The date of the first (last) day of the year, if year is available but day and month are missing;
- A very early (late) date, e.g., 01JAN1000 00:00hrs (01JAN3000 23:59hrs), if the date is completely missing.

5.1.4 Post therapies date imputation

Not applicable.

5.1.5 Other imputations

5.1.5.1 eDiary data

The eDiary includes the following clinical outcome assessments:

- Incidence of headache (i.e., migraine with or without aura or non-migraine headache)
- Time of onset of headache
- Time of resolution of headache
- Pain severity per headache
- Symptoms (e.g., nausea, vomiting, photophobia, phonophobia)
- Presence of aura
- Acute medication taken to treat headache, aura-only event, or both headache and aura

As well as, subject-reported outcomes (PROs) measures of [REDACTED], modified MIDAS, [REDACTED], [REDACTED]

Missing eDiary data in the calculation of monthly measurements about subjects' migraine and non-migraine headaches will be handled using the following method:

1. For monthly intervals with ≥ 14 days of eDiary days (including retrospective eDiary days) in each interval:
 - a. Monthly frequency measurements (including migraine days, [REDACTED], migraine attacks, acute medication use, acute migraine specific medication use etc.) will be prorated to 28-day equivalents. Prorated result does not need to be rounded.
[REDACTED]
2. For monthly intervals with < 14 days of eDiary use (including retrospective eDiary days), all monthly measurement will be set as missing and will be handled as described in [Section 5.1.5.3](#).

Briefly, handling missing and incomplete eDiary data is summarized by next rules:

Monthly Endpoint	Condition	Proration Method (does not need to be rounded)
------------------	-----------	--

Monthly frequency measurements (including migraine days, [REDACTED] acute headache medication treatment days)	If diary days in entire baseline or interval post baseline ≥ 14 (including retrospective eDiary days), then do proration; Else monthly measurement is set to missing [diary days is a day with all headache related questions completed retrospectively or not]	Number of observed migraine days * 28/ Number of information days in interval [information day is a diary day or headache day]
[REDACTED]	[REDACTED]	[REDACTED]

Missing PROs [REDACTED] mMIDAS [REDACTED] scheduled to be collected at office visit at certain assessment will not be imputed.

5.1.5.2 Missing Baseline Evaluation

Missing baseline evaluations will not be imputed.

All subjects included in the full analysis set will have baseline monthly rate or monthly average of migraine and non-migraine headaches related measurements after applying proration rule defined in [Section 5.1.5.1](#) since only subject with $\geq 80\%$ compliance of eDiary use during baseline will be eligible for randomization.

5.1.5.3 Missing Post-baseline Evaluation Treatment Period

Primary analysis of continuous efficacy endpoints during the 12-week DB treatment period will be conducted using the linear mixed effects repeated measures model on observed data without imputation (see [Section 5.4.1](#)).

In the sensitivity analysis on primary efficacy endpoint during the 12-week DB treatment period, missing continuous efficacy endpoints will be handled using baseline observation carried forward (BOCF) method, and multiple imputation (MI) with assumption of missing at random (MAR) and missing not at random (MNAR) (with control-based pattern imputation and treatment effect adjusted imputation), respectively. See below for more details.

In BOCF method, post-baseline missing continuous primary efficacy endpoint will be imputed using the baseline observed value. For example, if subject has all of the post-baseline values as missing, then all of the post-baseline values will be imputed using the observed baseline value.

In non-responder imputation (NRI) method, post-baseline missing dichotomous secondary [REDACTED] efficacy endpoints (responder [Yes/No] based on $\geq 50\%$, $\geq 53\%$, [REDACTED] reduction from baseline in monthly migraine days) during treatment period will be imputed as non-responder at each corresponding time point.

To address the impact of missing data on primary efficacy analysis, the amount of missing data, the distribution of missing data among treatment groups, and the reasons for missing data will be examined.

If the proportion of missing data in primary endpoint is high (e.g., > 20% for primary analysis at week 12) or if imbalance occurs amongst the treatment groups, further analysis will be performed to

- examine the frequency and reason of missing data
- determine if there are any patterns in the missing data
- distinguish true missing values from other unknown values (e.g., due to measurement or sample processing error)

Additional sensitivity analyses, including those based on alternative missing data assumptions, will be performed as deemed appropriate and necessary

